4.3. Withdrawal Criteria and Procedures for the Patient

Each patient is free to withdraw from the study or discontinue from the IMP at any time, without prejudice to their continued care. Patients must be withdrawn from the IMP and/or study if any of the following events occur:

1. Patient withdraws consent or requests discontinuation from the IMP or withdrawal from the study for any reason.
2. Patient develops an illness that would interfere with his/her continued participation.
3. Patient is noncompliant with the study procedures and assessments or administration of IMPs in the opinion of the investigator.
4. Patient takes prohibited concomitant medications as defined in this protocol.
5. A female patient has a confirmation of pregnancy during the study from a positive pregnancy test.
6. The sponsor requests withdrawal of the patient.
7. Patient experiences an adverse event or other medical condition which indicates to the investigator that continued participation is not in the best interest of the patient.

Patients should be treated with standard of care after withdrawal from or termination of the study as appropriate.

Investigators should attempt to obtain information on patients in the case of withdrawal from the study or discontinuation from IMP. Results of any evaluations and observations, together with a narrative describing the reason(s) for withdrawal from the study or discontinuation from IMP, must be recorded in the source documents. The case report form (CRF) must document the primary reason for withdrawal from the study or discontinuation from IMP.

For information regarding how the study will define and address lost to follow-up patients to help limit the amount and impact of missing data, see [Appendix F](#).

If the reason for withdrawal from the study or discontinuation from IMP is an adverse event and/or clinically significant abnormal laboratory test result, monitoring will be continued as applicable (eg, until the event has resolved or stabilized, until the patient is referred to the care of a health care professional, or until a determination of a cause unrelated to the IMP or study procedure is made). The specific event or test result (including repeated test results, as applicable) must be recorded both on the source documentation and in the CRF; both the adverse events page and the relevant page of the CRF will be completed at that time.

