3. ANALYSIS SETS

3.1. Intent-to-Treat Analysis Set

The intent-to-treat (ITT) analysis set will include all randomized patients.

In the ITT analysis set, treatment will be assigned based on the treatment to which patients were randomized, regardless of which treatment they actually received.

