5.2. Patient Disposition

Patients screened, patients screened but not randomized, and the reasons the patients were not randomized will be summarized only for the overall group using patient counts.

Patients in the ITT analysis set, patients in the ITT analysis set but not treated, patients in the double-blind safety analysis set, double-blind mITT analysis set, and per-protocol analysis set, patients who complete the double-blind treatment period, patients who withdraw from the double-blind treatment period, patients in the open-label safety analysis set and open-label mITT analysis set, patients who complete treatment, patients who withdraw from treatment, patients who complete the study, and patients who withdraw from the study will be summarized using descriptive statistics. Patients who withdraw from treatment and patients who withdraw from the study will also be summarized using descriptive statistics by reason for withdrawal. The denominator for calculating the percentages will be the number of patients in the ITT analysis set.

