The **weekly number of days** of efficacy variables (e.g., days of headache with at least moderate severity, migraine days) for each week during the 4-week period after the 1st dose of study drug will be derived and normalized to **7** days equivalent using the following formula.

$$\frac{\sum \text{Days or hours of efficacy variable during the 7 days period}}{\sum \text{Days with assessments recorded in the eDiary for the 7 days period}} \times 7 \quad (6)$$

The mITT analysis sets will be used for all efficacy analyses. Summaries will be presented by treatment group as randomized, unless otherwise noted. For the double-blind treatment period, summaries will be presented for the following treatment groups: placebo, fremanezumab quarterly, and fremanezumab monthly. For the open-label treatment period, summaries will be

presented by migraine classification (ie, CM, EM, and all), double-blind treatment group (ie, placebo, fremanezumab 675 mg/placebo/placebo, fremanezumab 675/225/225 mg, fremanezumab 225/225/225 mg, all fremanezumab), and overall (ie, total). Descriptive statistics for all efficacy data will be presented by month (or week) and over 12-week period for the double-blind period and the open-label period.

The primary and secondary endpoints analysis listed in Section 6.2.1 and Section 6.3 will be repeated for the per-protocol analysis set.

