6.2.3.2. Analysis with Multiple Imputation Method

Sensitivity analysis will be performed by imputing missing migraine days of months 1-3 using multiple imputation method. The data will be processed by the following steps.

- If a patient has partial electronic headache diary data (ie, <28 days) for a month, that month’s value will be considered missing before the MI procedure.
- For the patients in the fremanezumab treatment group who are early terminated with reasons of adverse event or lack of efficacy, they will be assigned to placebo group so their missing values will be imputed using data from the placebo treated patients
- Run SAS PROC MI procedure to create 100 complete datasets.

The following SAS code pertains to the MI analysis:

```
PROC MI DATA=XXX SEED=SEED OUT=MI_OUT NIMPUTE=100
MAXIMUM=. . . . . 28 28 28 MINIMUM=. . . . . 0 0 0;
CLASS TREAT GENDER REGION TRTFAIL MIGCLASS;
FCS REG (AVALMI1=TREAT GENDER REGION TRTFAIL MIGCLASS
BASE YOD/DETAILS) NBITER=100;
FCS REG (AVALMI2=TREAT GENDER REGION TRTFAIL MIGCLASS
BASE YOD AVALMI1/DETAILS) NBITER=100;
FCS REG (AVALMI3=TREAT GENDER REGION TRTFAIL MIGCLASS
BASE YOD AVALMI1 AVALMI2/DETAILS) NBITER=100;
VAR TREAT GENDER REGION TRTFAIL MIGCLASS YOD BASE
AVALMI1 AVALMI2 AVALMI3;
RUN;
```

- Within each imputed data set, for a patient who has partial, say X ($X < 28$) days , electronic headache diary data in a month, the monthly value will be replaced by
- $\sum(\text{observed days}) + (28 - X) * \text{imputed value} / 28$
- The monthly average number of migraine days *during the 12-week double-blind period* after the 1st dose of study drug will be the average of month 1, month 2 and month 3 values.

Each dataset will be analyzed using the same ANCOVA model as described in Section 6.2.2. The LS means and standard errors from each analysis will be output to a SAS data set. SAS MIANALYZE procedure will be used to generate the final LS means (\pm SE) for the treatment groups and the treatment differences (fremanezumab - placebo) as well as p-values associated with treatment differences. Ninety-five percent CIs for the LS means differences between each

Statistical Analysis Plan

fremanezumab treatment group (monthly dose and quarterly dose) and placebo will be constructed.

```
ODS OUTPUT DIFFS=MIXED_OUT;  
PROC MIXED DATA=UPDATED_MI_OUT METHOD=REML;  
BY _IMPUTATION_;  
CLASS TREAT GENDER REGION TRTFAIL MIGCLASS;  
MODEL CHG=BASE YOD TREAT GENDER REGION TRTFAIL MIGCLASS  
TREAT*MIGCLASS;  

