LSMEANS TREAT/DIFF;  
RUN;
```

The output dataset from the above SAS code will contain the estimate of the mean difference and the standard error of the estimate from each of the 100 datasets. SAS procedure, PROC MIANALYZE, will be used to generate an overall p-value and 95% CI for the treatment difference. The following SAS code may be used.

```
ODS OUTPUT PARAMETERESTIMATES=PARMEST;  
PROC MIANALYZE DATA=MIXED_OUT ALPHA=0-.05 THETA0=0;  
BY TRTN;  
MODELEFFECTS ESTIMATE;  
STDERR=STDERR;  
RUN;
```

This sensitivity analysis will be performed on the ITT analysis set.

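### The only ITT efficacy analysis imputes never-dosed fremanezumab patients from the fremanezumab arm, a small lean toward the drug that one sentence in SAP 6.2.3.2 would remove

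*SAP*

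**What the plan says.** SAP 6.1 sets the default population: "The mITT analysis sets will be used for all efficacy analyses". The primary ANCOVA and the MMRM follow it, and the primary and secondary analyses are repeated on the per-protocol set. The multiple imputation analysis in SAP 6.2.3.2 is the exception: "This sensitivity analysis will be performed on the ITT analysis set".

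SAP 3.1 defines that set: "The intent-to-treat (ITT) analysis set will include all randomized patients". Patients are labelled as randomized, whatever they received. SAP 3.2 requires at least one dose and at least 10 days of post-baseline assessment for the double-blind mITT set. ITT therefore adds back the patients who were never dosed and those with too few diary days.

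The placebo rule is the second bullet of 6.2.3.2. It opens "For the patients in the fremanezumab treatment group who are early terminated with reasons of adverse event or lack of efficacy" and continues "they will be assigned to placebo group so their missing values will be imputed using data from the placebo treated patients". For everyone else the source of the imputed values is set by the PROC MI code, whose first regression begins "FCS REG (AVALMI1=TREAT GENDER REGION TRTFAIL MIGCLASS". The regressions for months 2 and 3 also contain TREAT.

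The SAP allows for never-dosed patients. Its disposition table in 5.2 has a row for "patients in the ITT analysis set but not treated". No rule in 6.2.3.2 mentions them.

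**The concern.** The multiple imputation analysis is the only place where the patients excluded from mITT re-enter an efficacy comparison. Its use is to show whether leaving them out flattered the drug. Under SAP 4.4, month 1 starts at the first dose, so a never-dosed patient has no post-dose diary window and all three monthly values are imputed. Unless the termination is coded to one of the two named reasons, those values come from a model fitted with the patient labelled as fremanezumab. The analysis then credits a drug effect to someone who received no drug. For this group it builds in the effect that it ought to test.

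**Working it through.** **Inputs from the documents.** Planned difference 1.8 days, SD 6 days, alpha 0.05, 90% power, 235 evaluable and 268 randomized per group, 12% discontinuation (SAP 2.4; Protocol 9.1).

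**Assumption.** The share of an active arm that is never dosed is not given. I take 0.5% to 2%.

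**Reproducing the plan's figures.** A two-sided comparison of two means with difference 1.8 and SD 6 needs 234 per group by the normal approximation and 235 by the t-test (power 0.9007), or 705 in total. Allowing for 12% discontinuation, 235 / 0.88 = 267.05, rounded up to 268 per group, or 804 in total. The stated figures reproduce.

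**Following one never-dosed fremanezumab patient through 6.2.3.2.**
1. Not terminated for adverse event or lack of efficacy: TREAT stays fremanezumab.
2. No post-dose diary days: months 1, 2 and 3 are all missing.
3. Each month is imputed from a regression containing TREAT, so its expected value includes the fremanezumab effect.
4. The partial-month replacement formula, with X = 0 observed days, returns 0 + (28 - 0) x imputed / 28, which is the imputed value itself. No observed data offset it.
5. The ANCOVA counts the patient in the randomized fremanezumab arm.

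**Size.** Moving these patients to placebo for imputation changes the expected difference by

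shift = (share never dosed) x (share of the 12 weeks imputed) x 1.8, with the second factor equal to 1.

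| Share never dosed (assumed) | Patients of 268 | Shift, days | Expected difference, days | Nominal power at 268 per group |
|---|---|---|---|---|
| none | 0 | 0 | 1.800 | 0.935 |
| 0.5% | 1.3 | 0.005 x 1.8 = 0.009 | 1.791 | 0.933 |
| 1% | 2.7 | 0.01 x 1.8 = 0.018 | 1.782 | 0.930 |
| 2% | 5.4 | 0.02 x 1.8 = 0.036 | 1.764 | 0.926 |

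As a share of 1.8 days the shift is 0.5% to 2%. The standard error of one difference is 6 x sqrt(2/268) = 0.52 day, so the largest shift is 0.036 / 0.52, about 7% of one standard error.

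**The case against.** The strongest objection is size. Randomization and the first dose both fall at visit 2 (Protocol Appendix B), so few patients should be randomized and not treated, and the disposition row may be a standard line. A never-dosed patient who left for an adverse event before dosing would already be covered by the rule. All of this stands and is why the point is minor. It does not make the imputation right for those who remain.

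A reader might go further and infer that patients withdrawn for a barred drug are wrongly imputed in the same way. Protocol 4.3 lists that as a separate withdrawal criterion: "Patient takes prohibited concomitant medications as defined in this protocol". The documents do not support calling this an error:
- Quarterly patients receive all their double-blind active drug at visit 2, so leaving afterwards costs them only placebo injections.
- For monthly patients, the mean half-life of 32.2 to 36.2 days (Protocol 1.2.2.1) implies, under simple first-order decay, that 0.5^(28/32.2) = 0.55 to 0.5^(28/36.2) = 0.585 of the drug remains after 28 days.
- A patient who starts another preventive may do better or worse than placebo, so the direction of any bias is not established.
- Observed diary days are kept, and later months are conditioned on earlier ones.

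A reader might also apply the whole 12% discontinuation rate and arrive at a shift of up to 0.12 x 1.8 = 0.22 day. That would require every leaver to fall outside the rule, to miss all 12 weeks and to have no residual effect. It also mixes in consent withdrawal, loss to follow-up and other reasons that this point does not concern.

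Nor is it right that departed patients are stress-tested nowhere else. SAP 6.3.1.1 counts any early discontinuation as non-response for the 12-week responder endpoint. What is unique to 6.2.3.2 is the patients whom mITT excludes.

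**Conclusion.** The point holds for fremanezumab patients who received no study drug. The stated rule and code impute them from the treated fremanezumab arm unless their termination is coded as adverse event or lack of efficacy, and no other section changes that. If the drug works, the ITT sensitivity estimate is too favourable by 0.009 to 0.036 day of 1.8. That range rests on an assumed never-dosed share of 0.5% to 2% and on the planned effect of 1.8 days. The primary mITT analysis is not affected, and a shift of this size would rarely alter a conclusion. It is worth correcting because it concerns patients whom only this analysis brings back.

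The handling of prohibited-medication withdrawals is an estimand choice on which statisticians can differ. One detail merits a check. Protocol 4.3 has withdrawals with several reasons recorded as adverse event if one of the reasons is an adverse event. It makes an exception where an event not severe enough to warrant discontinuation calls for a barred drug: the recorded reason is then the need for that drug. Such patients fall outside the placebo rule, perhaps unintentionally.

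**What to change.** In the second bullet of SAP 6.2.3.2, add that fremanezumab patients who received no study drug are also assigned to placebo for imputation, whatever the recorded reason, with the randomized label used in the ANCOVA as SAP 3.1 requires. This takes one sentence and one flag in the imputation dataset. Protocol 9.5.4.2 leaves the imputation details to the SAP, so its text need not change. The change should be made before the first interim lock and unblinding, in line with SAP 2.5.2. The downside is a very slightly smaller sensitivity estimate.

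Separately, the sponsor may wish to state whether withdrawals recorded as prohibited medication under the Protocol 4.3 exception, where an adverse event led to the need, are meant to be imputed from their own arm or from placebo. Either can be defended if it is written down beforehand.

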6.2.3.3. ANCOVA Analysis

The ANCOVA analysis defined in Section 6.2.2 will be repeated as a sensitivity analysis using the actual stratification factors in the model.

6.2.4. Sub-Group Analyses

The ANCOVA analysis defined in Section 6.2.2 and MMRM analysis defined in Section 6.2.3.1 will also be applied for the following subgroups for the primary endpoint.

- age group (18-45 years, >45 years)
- sex (male, female)
- region (USA, Europe)
- country (Countries with less than 20 patients will be excluded from the subgroup analysis)
- migraine classification (CM, EM)

Statistical Analysis Plan

- 4 classes of preventive medications for migraine in the past not including valproic acid failures (yes, no)
- number of classes of preventive medications for migraine in the past failures (2, 3, 4)
- overuse of acute medication (yes, no)
- frequency of headache days at baseline for EM patients (4-9, 10-14)

An exploratory analysis for the primary endpoint will also be performed by adding the treatment-by-region interaction to the primary analysis model to test whether treatment effects are homogenous across regions.

6.3. Secondary Efficacy Endpoints and Analysis

The secondary endpoints to further demonstrate efficacy are as follows:

- proportion of patients reaching at least 50% reduction in the monthly average number of migraine days during the 12-week period after the 1st dose of fremanezumab
- mean change from baseline (28-day run-in period) in the monthly average number of headache days of at least moderate severity during the 12-week period after the 1st dose of fremanezumab
- mean change from baseline (28-day run-in period) in the monthly average number of migraine days during the 4-week period after the 1st dose of fremanezumab
- proportion of patients reaching at least 50% reduction in the monthly average number of migraine days during the 4-week period after the 1st dose of fremanezumab
- mean change from baseline (28-day run-in period) in the monthly average number of days of use of any acute headache medications during the 12-week period after the 1st dose of fremanezumab
- mean change from baseline (28-day run-in period) in the number of headache days of at least moderate severity during the 4-week period after the 1st dose of fremanezumab

6.3.1. Electronic Headache Diary Data

6.3.1.1. Definition

The percent reduction in the monthly average number of migraine days during the 12-week period after the 1st dose of fremanezumab will be calculated by formula (4) in Section 6.1. The patient is considered as a responder reaching 50% reduction if his/her percent reduction is 50% or more. If a patient is early discontinued from the study, he/she will be counted as a non-responder.

The percent reduction in the monthly average number of migraine days during the 4-week period after the 1st dose of fremanezumab will be calculated by formula (4) where the postbaseline value will be the number of migraine days prorated to 28 days for month 1. If the patient has 50% reduction or more in month 1, he/she will be considered a responder during the 4-week period after the 1st dose of fremanezumab.

The change from baseline in the monthly average number of headache days of at least moderate severity and the change from baseline in the monthly average number of days of use of any acute headaches medications during the 12-week period after the 1st dose of fremanezumab will be derived similar to the primary efficacy variable using the electronic diary data collected through the corresponding headache diary questions. The baseline values and the postbaseline values will be derived using formula (3) and (1) in Section 6.2.1, and the change is calculated as *postbaseline value – baseline value*.

The change from baseline in the monthly average number of migraine days and the change from baseline in the number of headache days of at least moderate severity during the 4-week period after the 1st dose of fremanezumab will be calculated using formula (2) and (1) in Section 6.2.1, and the change is calculated as *postbaseline value – baseline value*.

6.3.1.2. Analysis

The change from baseline secondary efficacy endpoints will be analyzed similarly as the primary efficacy endpoint. For the proportion of responders, a logistic regression model will be used with the following effects: treatment, gender, region, special group of treatment failure (Yes or No), and migraine classification (ie, CM or EM). The stratification factors (as randomized) will be used in the model. The odds ratios, 95% CIs for odds ratios, and p-values will be presented for each fremanezumab treatment group (monthly dose and quarterly dose).

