- h. At the time of screening, the patient must have documented inadequate response to 2 to 4 classes of prior preventive migraine medications (as defined in [Appendix H](#)) within the past 10 years (in medical chart or by treating physician’s confirmation; see [Appendix I](#) for acceptable documentation of previous treatment failure). Inadequate response to prior preventive migraine medications (including valproic acid) is defined as: no clinically meaningful improvement per treating physician’s judgment, after at least 3 months of therapy at a stable dose considered appropriate for migraine prevention according to accepted country guidelines, or when treatment has to be interrupted because of adverse events that made it intolerable for the patient, or the medication (as defined in [Appendix H](#)) is contraindicated or unsuitable for the prophylactic treatment of migraine for the patient. The 3- month period does not apply if the drug is intolerable or contraindicated. If onabotulinumtoxinA is the previous preventive medication, at least 2 sets of injections and 3 months must have passed since the last set of injections prior to the screening visit.
- i. The patient agrees not to initiate any preventive migraine medications (as defined in [Appendix H](#)) during the run-in period, double-blind treatment period, and open-label period. At the screening visit, at least 5 half-lives of these medications must have passed since the patient has been on any migraine preventive medication as defined in [Appendix H](#).
- j. Other prescription medications not in [Appendix H](#) must have been on stable doses for at least 2 months at the screening visit with no expectation to change during the double-blind treatment period of the study.
- k. The patient demonstrated compliance with the electronic headache diary during the run-in period by entry of headache data on a minimum of 24 days cumulative during the run-in period (~85% diary compliance).
- l. Women may be included only if they have a negative serum beta-human chorionic gonadotropin (β -HCG) test at screening, are sterile, or postmenopausal. Definitions of sterile and postmenopausal are given in [Appendix E](#).

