9.5.4.3. Secondary Efficacy Analysis

The continuous secondary efficacy endpoints will be analyzed similarly as the primary efficacy endpoint. For the proportion of responders, defined as 50% or more reduction from baseline in the monthly average number of migraine days, a logistic regression model will be used with the following effects: treatment, gender, region, special group of treatment failure (Yes or No), and migraine classification (ie, CM or EM). The odds ratios, 95% confidence intervals for odds ratios, and p-values will be presented for each fremanezumab treatment group (monthly dose and quarterly dose).

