2.4. Sample Size and Power Considerations

In the Phase 2b study for CM (study LBR-101-021), the treatment difference between 675/225/225 mg and placebo in change from baseline in monthly average migraine days was 2.1 days (standard deviation [SD]=5.2 days). In the phase 2b study for EM (study LBR-101-022), the treatment difference between 225 mg monthly dose and placebo in change from baseline in monthly average migraine days was 2.7 days (SD=4.1 days). In the Phase 3 study for CM (study TV48125-CNS-30049), the treatment differences to placebo in change from baseline in monthly average migraine days were 1.7 days and 1.8 days for the quarterly dose and the monthly dose, respectively (SD=5.4 days). In the Phase 3 study for EM (study TV48125-CNS-30050), the treatment differences to placebo in change from baseline in monthly average migraine days were 1.3 days and 1.5 days for the quarterly dose and the monthly dose, respectively (SD=3.4 days). Combining the information above, a treatment difference of 1.8 days is used. Considering the patient population is different from the previous studies, a SD of 6 days is used to account for the complexity and uncertainty of this study.

A sample size of 705 (235 patients per treatment group) evaluable patients completing the study is needed for 90% power to show a 1.8 difference in migraine days (assuming a common SD of 6 days) at an alpha level of 0.05. Assuming a 12% discontinuation rate, 268 patients per treatment group will be randomized in the study.

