6.2.2. Primary Efficacy Analysis

The hypothesis testing for the primary analysis is:

$$H_o : \delta_1 = \delta_2 \quad vs \quad H_a : \delta_1 \neq \delta_2$$

where δ_1 and δ_2 are the estimates of mean change from baseline in the monthly average number of migraine days for the fremanezumab treatment group and the placebo group respectively. The estimated difference of fremanezumab monthly dose versus the placebo and fremanezumab quarterly dose versus the placebo will be tested following the pre-specified fixed sequence as described in Section 7.

The primary efficacy endpoint will be analyzed using an analysis of covariance (ANCOVA) method. The model will include treatment, gender, region, special group of treatment failure (Yes or No), migraine classification (ie, CM or EM), and treatment-by-migraine classification interaction as fixed effects, and baseline number of migraine days and years since onset of migraines as covariates. The stratification factors (as randomized) will be used in the model. The treatment comparison between each fremanezumab treatment group (monthly dose and quarterly dose) and placebo for monthly average migraine days will be conducted under this model using the estimate statement. Ninety-five percent confidence intervals (CIs) will be constructed for the least square (LS) means differences between each fremanezumab treatment group (monthly dose and quarterly dose) and placebo.

Note: Special treatment failure group defined as patients who must have had inadequate response to valproic acid. In addition, patients in the special treatment failure group must have had inadequate response to 2 to 3 other classes of migraine preventive medications as defined in Appendix H of the protocol.

Type I error will be controlled for treatment comparisons by using Hochberg's method (see Section 7).

The following sample SAS code pertains to the primary analysis.

```
ODS OUTPUT DIFFS=XXX LSMEANS=XXX TESTS3=XXX;
```

```

PROC MIXED DATA=XXX;
    CLASS TREAT GENDER REGION TRTFAIL MIGCLASS;
    MODEL CHG=BASE YOD TREAT GENDER REGION TRTFAIL MIGCLASS
    TREAT*MIGCLASS/S;
    LSMEANS TREAT/PDIFF CL ALPHA=0.05;
RUN;

```

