7. MULTIPLE COMPARISONS AND MULTIPLICITY

The Hochberg's method along with hierarchical testing procedure for multiple comparisons between treatment groups (2 comparisons: fremanezumab monthly dose compared with placebo and fremanezumab quarterly dose compared with placebo) for the primary and secondary endpoint analyses will be used to maintain the experiment-wise type I error of 5%. In the primary analysis, according to the Hochberg's method, if the null hypothesis is rejected for both the fremanezumab monthly and quarterly treatment groups at an alpha level of 5%, then no adjustment to the alpha level will be performed and both comparisons will be declared as statistically significant. The secondary variables will then be tested in the order as specified in Section 6.3 for both the fremanezumab monthly and quarterly treatment groups using the same procedure as the primary analysis. If the null hypothesis is not rejected for 1 of the doses at an alpha level of 5%, then the other dose will be tested using an alpha level of $5\%/2=2.5\%$, and the sequential testing will stop.

No multiplicity adjustments will be made for exploratory efficacy analyses.

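### The logistic model for the two secondary 50% responder endpoints omits baseline migraine days; adding it is an optional, cheap improvement worth about 0 to 2.5 points of power at the first secondary test

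*SAP*

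**What the plan says.** SAP 6.3.1.2 fits the responder endpoints by logistic regression "with the following effects: treatment, gender, region, special group of treatment failure (Yes or No), and migraine classification (ie, CM or EM"). Protocol 9.5.4.3 prespecifies the same five effects ("a logistic regression model will be used with the following effects: treatment, gender, region", then treatment-failure group and migraine classification). The primary ANCOVA in SAP 6.2.2 also has "baseline number of migraine days and years since onset of migraines as covariates", and the change-from-baseline secondaries follow the ANCOVA. The two responder endpoints are therefore the only inferential secondaries without baseline adjustment, and neither document gives a reason.

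The baseline value exists for every eligible patient. Protocol 4.1 criterion k requires "entry of headache data on a minimum of 24 days cumulative during the run-in period", Protocol Section 4 grants no waivers, and formula (3) in SAP 6.1 converts the run-in diary to a 28-day count.

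On order, SAP Section 7 says "The secondary variables will then be tested in the order as specified in Section 6.3", and Section 6.3 lists the 12-week 50% responder endpoint first. If either dose misses 5% there, the sequence stops. On dropouts, SAP 6.3.1.1 says of the 12-week endpoint: "If a patient is early discontinued from the study, he/she will be counted as a non-responder".

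**The concern.** A responder must lose at least half of the baseline migraine days, so the fall required depends on baseline. Unless the mean fall rises by about half a day per extra baseline day, baseline still predicts response within CM and within EM. The classification term captures only part of this: under the run-in criteria in SAP 2.1, qualifying migraine days can run from 4 to 14 in EM and from 8 to 28 in CM.

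Leaving out a prognostic baseline value from a logistic model pulls the treatment odds ratio towards 1 and can cost power. The position of the test is what makes a small loss worth noticing, because a miss by either dose at this first secondary step also closes the five later secondary endpoints.

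**Working it through.** **The plan's own figure.** With a difference of 1.8, SD 6 and two-sided 5%, n per group = 2 × 6² × (1.960 + 1.282)² / 1.8² = 233.5, so 234. The t-test version needs 235 (90.07% power). 235 / (1 − 0.12) = 267.05, so 268 per group and 804 in all, as stated. This concerns the primary endpoint only. No power is stated for the responder endpoint.

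**Why baseline can matter within EM.** Take placebo patients with a mean fall of 2.6 (Protocol 1.2.2.2) and SD 3.4 (SAP 2.4), and suppose the fall is unrelated to baseline.
- Baseline 5 days: a fall of 2.5 is needed; Φ((2.6 − 2.5)/3.4) = 51%.
- Baseline 13 days: a fall of 6.5 is needed; Φ((2.6 − 6.5)/3.4) = 13%.

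If instead the mean fall rises by 0.5 day per baseline day around an assumed mean of 9, the expected falls are 0.6 and 4.6. Both patients are then 1.9 days short of the target, and baseline tells us nothing more.

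**Simulation inputs from the documents.** 268 per arm and 12% discontinuation ("Assuming a 12% discontinuation rate, 268 patients per treatment group will be randomized in the study"), with those patients set to non-response; CM and EM 50:50; SD of change 3.4 (EM) and 5.4 (CM); differences from placebo, monthly/quarterly, 1.5/1.3 (EM) and 1.8/1.7 (CM); placebo fall 2.6 (EM) and 2.9 (CM). The CM placebo figure is for headache days of at least moderate severity and is used as a stand-in.

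**Inputs assumed.** Baseline mean (SD) 9 (2.5) in EM and 16 (4.5) in CM, truncated to 4–14 and 8–28; discontinuation unrelated to outcome; and the slope, meaning the extra mean fall per extra baseline day. The residual SD was set so that the total SD of change stays at 3.4 or 5.4.

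**Result.** Probability that both doses reach 5%, with CM/EM in both models, 10,000 trials per row, paired Monte Carlo SE of the gain 0.08 to 0.25 points:

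| Assumed slope | As planned | Baseline added | Gain |
|---|---|---|---|
| 0 | 67.3% | 69.4% | +2.1 |
| 0.15 | 69.9% | 71.3% | +1.4 |
| 0.3 | 73.5% | 74.1% | +0.6 |
| 0.5 | 78.0% | 78.0% | 0 |
| 0.65 | 81.0% | 81.3% | +0.3 |
| 0.8 | 85.1% | 85.7% | +0.6 |

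At slope 0 the simulated responder rates were 21.1% (placebo), 32.1% (monthly) and 30.9% (quarterly). The mean SE of the log odds ratio rises from 0.2026 to 0.2076, but the estimate moves further from zero, and the squared ratio of mean z is 1.047.

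**Sensitivity.**
- Repeat runs gave gains of 1.9 to 2.5 at slope 0, 0.4 to 0.8 at 0.3, and −0.1 to +0.3 at 0.5.
- Narrower baseline spread (SD 1.8 and 3.0): +1.5, +0.5, 0, 0 and +0.5 at slopes 0, 0.15, 0.3, 0.5 and 0.8.
- Residual rather than total SD held at 3.4 and 5.4: +2.2, +1.4, +0.3, 0 and +0.8 at the same slopes.
- Slopes of 0.73 in EM and 0.3 in CM: 79.9% under both models.
- Planning values of 1.8 and SD 6: about +2 at slope 0 and +0.4 at 0.25.
- Discontinuation below the plan's 12%, at slope 0: +3.5 with 6%, and +2.8 to +4.7 across runs with none.
- No treatment effect: rejection rate per dose 4.6 to 5.1% as planned and 4.7 to 4.9% adjusted.

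The 4-week responder endpoint and the covariate years since onset were not simulated.

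**The case against.** The plan's choice can be defended. The outcome is already scaled to each patient's own baseline, migraine classification is itself defined from run-in counts, and protocol and SAP agree on the model. The log for Amendment 01 shows that this logistic model replaced a Cochran-Mantel-Haenszel test at the VHP's request. The correspondence is not available, so whether the covariate list was part of that request is unknown. The largest gain also needs a slope near 0, which is unlikely: baseline is a single 28-day count, so regression to the mean alone makes patients with high counts fall further. All of this stands. It makes the change optional, but it does not show that baseline is uninformative.

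Three stronger readings are tempting, and the documents do not support them.
- A reader might infer that the responder test is invalid, or that the 90% power is undermined. Neither follows: the test keeps its size, and the 90% belongs to the primary ANCOVA, which already includes baseline.
- A reader might see a defect in "The stratification factors (as randomized) will be used in the model", since randomisation is stratified by country while the model lists region. SAP 4.5 pools the countries into two regions for analysis, both documents name region in the models, and the as-randomised wording is most naturally read against the repeat with actual factors in SAP 6.2.3.3. At most this calls for a one-line clarification.
- A reader might extend the covariate to every responder analysis. PGIC is not a change in migraine days, and the special treatment-failure subset may have only 120 patients, about 40 per arm. No benefit has been shown for these analyses.

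**Conclusion.** The omission is real and its effect is modest. With 12% of each arm counted as non-responders, adding baseline migraine days raises the chance that both doses pass the first secondary test by about 0 to 2.5 points. The gain is near zero at slopes of 0.3 to 0.5 and greatest at slope 0. The range rests on assumed slopes and an assumed baseline spread; it is not a figure from the documents, and it would be higher at slope 0 if fewer patients discontinued. This is an optional, cheap improvement and not an error that must be corrected.

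**What to change.** Before the first interim database lock (SAP 2.5.2), add baseline number of migraine days, as derived by formula (3), to the logistic model in SAP 6.3.1.2 for the 12-week and 4-week 50% responder secondary endpoints. State that the odds ratio is then conditional on baseline, and list the departure from Protocol 9.5.4.3 in SAP Section 17. Because SAP 6.4.1.2 and 6.4.8.2 reuse this model, say there that the exploratory, subset and PGIC analyses keep the present five effects.

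No new data are needed. The costs are a short SAP revision, an odds ratio with a conditional interpretation, and a small declared departure from the model introduced at the VHP's request.
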